## 11.3 Final Analysis Plan

We will perform spectral analysis of resting state EEG before and after stimulation treatment and use a mixed ANOVA with the within subject factor session (immediately before first stimulation session and immediately after last stimulation session) and between subject factor treatment (sham, 10Hz tACS or 2 mA tDCS). Spectral analysis will be performed with multi-tapered estimation of the frequency spectrum followed by integration over the classical alpha EEG band (8-12 Hz). We will apply the same statistical analysis procedure for our primary outcome of AHRS, PANSS and BACS scores.

We will also use post-hoc paired or unpaired Student's t-test to identify the group or groups that differed. We will further control for multiple comparisons by using Bonferroni corrections.

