### **3.2 Study Outcome Measures**

#### **3.2.1 Primary Outcome Measures**

The Auditory Hallucination Rating Scale (*Attachment 3*) will be the primary outcome measure for this study. This rating will be administered at baseline, two weeks later at the screening visit, the first day of stimulation, last day of stimulation, at the one week and the one month follow up visits. We will compare the AHRS scores immediately before the first stimulation session and immediately after the last stimulation session as our primary outcome measure.

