#### **3.2.2 Secondary Outcome Measures**

We will compare alpha oscillation power from resting state EEG recordings from the screening visit and last day of stimulation. We will also collect EEG data at the one week and one month follow up visits. We will use these data to analyze alpha frequency activity as a pilot study for derivation of EEG biomarkers.

The Positive and Negative Syndrome Scale (PANSS) (*Attachment 5*) and Brief Assessment of Cognition in Schizophrenia (BACS) (*Attachment 12*) will also be secondary outcome measures for this study. These measurements will be taken at baseline, first day of stimulation, and last day of stimulation and at the one month follow up visit. We will compare the PANSS and BACS scores immediately before first stimulation session and immediately after last stimulation session as secondary outcome measures.

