### 2nd Screening Visit (Visit 2)

At the beginning of the 2nd screening visit, vitals will be taken and an EEG will then be administered. The EEG recording will include resting state data along with two auditory tasks. After each EEG, an EEG questionnaire (*Appendix U*) will be administered to document the participant's auditory experiences during the EEG tasks. The following questionnaires will then be administered to further check eligibility; Auditory Hallucination Rating Scale (AHRS) in order to document any change in auditory hallucination severity/frequency (*Attachment 3*). The AHRS scores from the initial screening visit and the current visit will be compared. If a change in score greater than 20% exists, then a 3rd screening visit will be scheduled for approximately 2 weeks later. If a change in AHRS score is less than or equal to 20% then the Simpson Angus Scale (SAS) (*Attachment 9*) and the Abnormal Involuntary Movement Scale (AIMS) (*Attachment 7*) will be administered as a baseline assessment of extrapyramidal syndromes or tardive dyskinesia due to antipsychotic medication use. In order to ensure proper assessment,

each AIMS administration will initially be recorded to be reviewed and scored by [name] until the researcher is deemed to have sufficient experience. At the end of the initial session, and once eligibility has been confirmed, a saliva sample will be collected (for testing of BDNF allele), the week of stimulation will be scheduled, and the participant will be paid.

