## **8 STUDY PROCEDURES/EVALUATIONS**

### **8.1 Clinical Evaluations**

During the initial session, researchers will collect demographics. Participant demographics include medical history and medication history. This information is used to confirm inclusion criteria and that no current alcohol and drug abuses or disorder exist.

Several clinical evaluations will be used throughout this study. These assessments are listed below and can be found in the attached documents.

- i. The Structured Clinical Interview for DSM-IV Axis I Disorders (SCID-I) is a semi-structured interview used to diagnosis major Axis I disorders. For this study, the SCID-I (First et al. 2004) will be administered at baseline in order to confirm a diagnosis of Schizophrenia or Schizoaffective Disorder.
- ii. The Auditory Hallucination Rating Scale (AHSR) is a structured interview, designed to assess different aspects of patient's auditory hallucinations. This assessment has 11 items and is rated on a scale of 0 – 4 based on the responses given by the patient. The AHSR will be administered at the baseline visit, the first day of stimulation, the last day of stimulation, and at the one week and one month follow up visits.
- iii. The Positive and Negative Syndrome Scale (PANSS) is a structured interview used to assess the symptom severity of patients diagnosed with schizophrenia. The PANSS (Kay et al. 1987) focuses on the positive and negative syndromes and their general severity. This scale will be administered the initial session, first day of stimulation, the last day of stimulation and at the one month follow up visit.
- iv. The Brief Assessment of Cognition in Schizophrenia (BACS) will be administered at baseline, day 5 of stimulation and at the week 5 follow-up session in order to monitor changes in participant cognition. This validated assessment (Keefe et al. 2004, Keefe et al. 2006) contains 6 tests that focus on verbal memory and learning, working memory, motor functioning, attention/processing speed, verbal fluency and reasoning and problem solving.

- v. The Simpson Angus Scale (SAS) (Janno et al. 2005) is a 10 item assessment of medication related extrapyramidal side effects. The SAS will be administered at the first day of stimulation to obtain a baseline assessment, and again at day 5 of stimulation and the week 5 follow-up session to monitor symptom severity or development for each participant.

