# 11 STATISTICAL CONSIDERATIONS

## 11.1 Study Hypotheses

### 11.1.1 Primary Objective

*Null hypothesis:* There is no difference in AHRS score immediately before first stimulation session and immediately after last stimulation session between treatment groups.

*Alternative hypothesis:* There is a difference in AHRS score immediately before first stimulation session and immediately after last stimulation session between treatment groups.

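### The planned mixed ANOVA tests AHRS change without adjusting for the Day-1 AHRS; with a common baseline slope, ANCOVA on that score is asymptotically at least as precise

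*Combined protocol and SAP*

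**What the plan says.** **Model.** Section 11.3 describes the analysis for EEG alpha power: "use a mixed ANOVA with the within subject factor session (immediately before first stimulation session and immediately after last stimulation session", with the three arms as between-subject factor. It then states: "We will apply the same statistical analysis procedure for our primary outcome of AHRS, PANSS and BACS scores". Paired or unpaired t-tests follow, and "We will further control for multiple comparisons by using Bonferroni corrections". It names no covariate, alpha level, number of comparisons or missing-data rule.

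**Question.** The null hypothesis in section 11.1.1 reads: "There is no difference in AHRS score immediately before first stimulation session and immediately after last stimulation session between treatment groups". Section 3.2.1 agrees: "We will compare the AHRS scores immediately before the first stimulation session and immediately after the last stimulation session".

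**Available covariate.** Section 8.1 says: "The AHSR will be administered at the baseline visit, the first day of stimulation, the last day of stimulation" (the acronym is transposed there). Section 7.3 places the Day-1 rating before the first stimulation.

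**Sample size.** Section 11.2 makes no calculation. It expects 16 per arm to suffice for a large effect and gives no number for it.

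**Discontinuation.** Section 5.4.3 asks people who withdraw voluntarily to carry on with the planned evaluations. For anyone discontinued because of an AE or SAE it provides for safety data, and in every case for safety follow-up. Section 9.1 lists the safety assessments as vital signs, PANSS and the adverse effects questionnaire. Section 7.3 lists no AHRS on Days 2 to 4.

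**EEG timing.** Section 3.2.2 says: "We will compare alpha oscillation power from resting state EEG recordings from the screening visit and last day of stimulation". Section 7.2 agrees for the second screening visit, where "vitals will be taken and an EEG will then be administered", and repeats the recording at a third or fourth visit; Appendix A also shows it at screening. Sections 8.2.2 and 14.3 put an EEG on Day 1 instead, and section 11.3 refers to the time just before the first session. On Day 5, section 7.3 records the EEG before that day's stimulations, whereas section 11.3 refers to the time after the last one.

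**The concern.** With two sessions, the session-by-treatment term is a comparison of mean change between arms. A change score fixes the slope of post on pre at 1. Where the true slope is lower, the change score carries baseline noise that a fitted slope would remove. In a pilot of 16 per arm, whose purpose includes preliminary efficacy data on AHRS, precision may be given up although the covariate is already in hand.

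The follow-up gap affects the same analysis. A two-session ANOVA uses only people with both AHRS scores. Someone discontinued involuntarily before the Day-5 rating has no planned post-stimulation AHRS and drops out of the primary comparison.

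**Working it through.** **There is no plan figure to reproduce.** The documents state no power, alpha, SD, correlation or numeric effect. From the documents: 3 arms, 16 per arm, two AHRS time points. Assumed: everything else.

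**Step 1: the planned test is a change-score test.** On a generated 3 x 16 data set, the session-by-treatment F and the one-way F on change were identical (2.9357).

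**Step 2: variance with a common slope.** Let the Day-1 SD be 1, the post SD k and the correlation rho.

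- Change: 1 + k² − 2·rho·k
- ANCOVA residual: k²(1 − rho²)
- Difference: (1 − rho·k)², which is never negative

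With k = 1 and rho = 0.5, change has 1.00 and ANCOVA 0.75, a ratio of 0.75. Estimating the slope multiplies the ANCOVA variance by 1 + 1/43 = 1.023 on average, giving 0.767. The two are tied when rho·k = 1: with k = 1.25 and rho = 0.8, change has 1 + 1.5625 − 2 = 0.5625 and ANCOVA 1.5625 × 0.36 = 0.5625.

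**Step 3: power.** Simulation, 20,000 trials per setting, only tACS shifted, by 0.8 Day-1 SD. Each cell gives change / ANCOVA in %. The contrast is tACS-sham with pooled error (45 or 44 df). The 0.0167 level is 0.05/3, assuming three pairwise comparisons.

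| k | rho | Omnibus, 0.05 | Contrast, 0.05 | Contrast, 0.0167 |
|---|---|---|---|---|
| 1 | 0.3 | 46 / 64 | 46 / 63 | 29 / 44 |
| 1 | 0.5 | 61 / 73 | 60 / 71 | 42 / 54 |
| 1 | 0.7 | 84 / 89 | 82 / 87 | 67 / 74 |
| 1 | 0.8 | 96 / 97 | 94 / 95 | 86 / 89 |
| 1.25 | 0.5 | not computed | 49 / 52 | 32 / 35 |
| 1.25 | 0.7 | not computed | 69 / 69 | 52 / 52 |
| 1.25 | 0.8 | not computed | 84 / 83 | 70 / 69 |

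With a common slope, simulated type I error was 4.7 to 5.3% for both methods.

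**Step 4: unequal slopes.** With arm slopes b_a and residual variance s2, 16 times the contrast variance is the sum over the two arms of (b_a − 1)² + s2 for change, and of (b_a − mean b)² + s2 for ANCOVA with one pooled slope.

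| Slopes (sham, tACS, tDCS) | s2 | Change | ANCOVA | Ratio |
|---|---|---|---|---|
| 1, 1, 0 | 0.5 | 1.000 | 2 × (1/9) + 1 = 1.222 | 1.22 (simulated 1.27) |
| 1, 1, 0.5 | 0.4 | 0.800 | 0.856 | 1.07 (simulated 1.10) |
| 0.7, 0.7, 0.4 | 0.5 | 1.180 | 1.020 | 0.86 (simulated 0.88) |

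In the 1, 1, 0 setting, power depends on the comparator. The pooled-slope ANCOVA contrast has about 75%, against 87% for a two-arm t-test on change but 72% for the 45-df contrast. The omnibus test has about 77% for ANCOVA and 73% for change. The reason is that the change variances by arm are 0.5, 0.5 and 0.5 + 1 = 1.5. Their mean of 0.833 overstates the error for tACS-sham, and the 45-df contrast is conservative (simulated type I error 1.5%). With arm-by-baseline terms, ANCOVA power is 86%.

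**Step 5: attrition, hypothetical.** If m of 16 in one arm are removed and their mean change is delta change-SDs worse than the full arm's, the completers' mean shifts by m·delta/(16 − m). That is 1 × 0.5/15 = 0.03 to 3 × 1/13 = 0.23. The shift cancels if the pattern is the same in both arms.

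**The case against.** The strongest reply is that this is a preference for efficiency, not an error. The trial is a pilot with no power claim for the analysis to miss. Every input to the gain is assumed, and the 20% stability screen in section 4 may raise the correlation and shrink the gain. This stands, and it limits the point to a recommendation.

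A reader might infer more than the documents support:

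- **That the planned test is invalid or inflates type I error.** With a common slope it holds its level.
- **That ANCOVA always wins.** The algebra needs a common slope and is asymptotic; the results above include a tie, a small loss and a 1.27 variance ratio. Nor does unequal slope always cost power: in the 1, 1, 0 setting ANCOVA loses to the two-arm t-test but not to the 45-df contrast or the omnibus test.
- **That section 5.4.3 bars AHRS after an involuntary discontinuation, or that the result will be biased.** The section is silent and does not forbid it. The documents give no dropout rate and no sign of differential removal.
- **That sections 5.3 and 5.4.2 flatly contradict each other on missed sessions.** Section 5.3 ends participation after two consecutive misses, while section 5.4.2 lists more than two missed stimulation sessions as a ground. Section 5.4.2 does not say its list is exclusive, so both could apply. The wording is unaligned rather than plainly contradictory.

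Section 11.3 also does not say which ANOVA effect is primary. Session by treatment is inferred from section 11.1.1.

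**Conclusion.** The point holds as a conditional efficiency improvement. Under a common slope and equal SDs, the simulated gain in the tACS-sham contrast at unadjusted 0.05 falls from about 17 points at rho 0.3 to 1 or 2 points at rho 0.8. It disappears near rho·k = 1. Whether this trial would gain cannot be known from the documents. The change is still worthwhile, because the covariate exists and the loss is small unless slopes differ strongly, which the sensitivity analysis can show.

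The gap in section 5.4.3 is real as a matter of planned data collection. Its effect on the estimate is hypothetical.

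**What to change.** **Section 11.3.** Suggested wording:

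> The primary analysis is an ANCOVA of AHRS after the last stimulation session, with arm as factor and AHRS just before the first session as covariate. An omnibus test of arm is followed by Bonferroni-corrected pairwise contrasts from the same model. The tACS-sham difference is reported with its 95% CI. A sensitivity analysis adds arm-by-baseline terms, with baseline centred at the overall mean.

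Use the same model for PANSS and BACS with their Day-1 scores. Extend it to alpha power only after sections 3.2.2, 7.2, 7.3, 8.2.2, 11.3, 14.3 and Appendix A agree on both the baseline and the Day-5 recording.

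*Cost:* protocol wording, one residual degree of freedom (44 instead of 45) and about 2% variance when adjustment brings nothing. With a common slope, using the model with interaction terms would cost about one point of power (69.9% against 71.1% at rho 0.5).

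**Section 5.4.3.** Extend the request to continue scheduled evaluations to all who stop stimulation and consent, worded consistently with sections 5.4.2 and 9.3.1, which speak of ending participation. Report by arm how many have no post-stimulation AHRS. *Cost:* one sentence and some visits that are already scheduled; the documents do not give their cost.

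**Sections 5.3 and 5.4.2.** Reconcile the missed-session wording. No rule is proposed here.

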Eligible participants who complete this clinical trial will have a total of 9 to 11 visits; an initial screening session, a 2nd screening session, (if needed) 2 more follow up screening sessions, 5 days of twice daily stimulation sessions, a one week and a one month follow up visit. The initial screening session will take approximately 2 hours, and each follow up screening session will take approximately 3 hours each. The first day of stimulation will take approximately 6 hours and days 2 through 4 of stimulation will take 4.5 hours each. The last day of stimulation will take about 9 hours. The one week follow up will take approximately 2.5 hours and the one month follow up will take approximately 5 hours. We estimate that total participant participation duration will be approximately 41 to 47 hours.

The primary objective is to conduct a pilot clinical trial to establish the feasibility of recruitment and implementation of the methodology and to collect preliminary efficacy data for the use of tACS by comparing AHRS scores immediately before the first stimulation session and

immediately after the last stimulation session in patients with schizophrenia or schizoaffective disorder. As a secondary objective we will assess the differential clinical effects of sham, 10 Hz and 2 mA tDCS on EEG measures of alpha oscillations.

In order to ensure symptom stability for each potential participant, there will be up to a 6 week period for the participant to achieve a stable AHRS score. The AHRS will be performed at 2 week intervals during screening. A stable score is defined as having less than or equal to 20% change. If the change between the first and second AHRS scores is less than or equal to 20%, then the participant will move on to the week of stimulation. If a stable score is not achieved at the second screening session, the participant will have two more opportunities at 2 week intervals during follow-up screening sessions to achieve a stable score. The participant will be paid for each session. If the participant does not achieve a stable score (if there remains a greater than 20% change in scores between consecutive AHRS administrations) by the end of the 6 weeks, the participant will not be eligible to continue participation.

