## **5 STUDY ENROLLMENT AND WITHDRAWAL**

### **5.1 Participant Inclusion Criteria**

In order to be eligible to participate in this study, a participant must meet all of the following criteria:

- DSM-IV diagnosis of schizophrenia, any subtype, or schizoaffective disorder, with refractory auditory hallucinations. Duration of illness >1 year
- 18-70 years old
- Clinically stable for at least 12 weeks, i.e. not requiring hospitalization or a change in level of care
- On current antipsychotic doses for at least 4 weeks
- Experience at least 3 auditory hallucinations per week.
- Stable auditory hallucinations as demonstrated by having less than or equal to 20% change in AHRS scores across a 2 week interval during the screening period.
- Capacity to understand all relevant risks and potential benefits of the study and to provide written informed consent, OR has a legal guardian who can provide informed consent on the patient's behalf with the patient providing written assent to participate.

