## 7.2 Enrollment/Baseline

### Initial Screening Visit (Visit 1, Day 0)

At the consent visit, participants will sign both a HIPAA authorization form and the consent form. Each form will be read to the participant by the researcher, and the participant will be given the time to ask any questions about the information discussed. The researcher will verify that the participant meets inclusion criteria. If the participant is female, she will be asked to provide urine for a pregnancy test. All participants (male and female) will be asked to complete a urine drug screening to determine eligibility for the study. Next, the SCID (*Attachment 6*) will be administered in order to confirm diagnosis of schizophrenia or schizoaffective disorder and to verify that the participant does not have active alcohol or illicit drug abuse or dependency. Once the diagnosis has been confirmed, demographic information will be collected, which will include a history of medication, alcohol, and drug use and information about symptom onset and baseline vitals will be taken. A short handedness questionnaire and a Belief about Treatments questionnaire will also be administered. Each participant will be asked a series of questions (*Appendix H*) to ensure that the consent form is fully understood. After consent has been obtained, a baseline Auditory Hallucinations Rating Scale (AHRS) will be administered to document hallucinatory severity and frequency. The 2nd screening visit will be scheduled for approximately 2 weeks later, and the participant will be paid.

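### Section 11.3 leaves unused the screening AHRS scores that every eligible randomised participant has; an ANCOVA on Day 1 and screening AHRS would probably be more precise, by an amount the documents cannot fix

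*Combined protocol and SAP*

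**What the plan says.** **Which scores are compared.** Section 3.2.1 defines the primary outcome: "We will compare the AHRS scores immediately before the first stimulation session and immediately after the last stimulation session as our primary outcome measure". Section 11.3 gives the model, first for EEG alpha power: a mixed ANOVA with a three-level arm factor and the "within subject factor session (immediately before first stimulation session and immediately after last stimulation session"). It then carries this over to the clinical scales: "We will apply the same statistical analysis procedure for our primary outcome of AHRS, PANSS and BACS scores". Differing groups are identified by post-hoc t-tests with Bonferroni correction. No covariate is named.

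**Which scores exist.** Section 3.2.1 says of the AHRS: "This rating will be administered at baseline, two weeks later at the screening visit, the first day of stimulation", and continues through the last stimulation day and both follow-ups. Section 4 says "The AHRS will be performed at 2 week intervals during screening". In section 7.2, at Visit 1, "a baseline Auditory Hallucinations Rating Scale (AHRS) will be administered to document hallucinatory severity and frequency"; at Visit 2, "The AHRS scores from the initial screening visit and the current visit will be compared". Section 5.1 makes stability an inclusion criterion: "less than or equal to 20% change in AHRS scores across a 2 week interval during the screening period". Section 7.3 adds a Day 1 rating before stimulation. In Appendix A, randomisation falls in the column where stimulation starts, after screening.

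The visit lists in sections 8.1 and 14.3 omit the second screening AHRS, but sections 3.2.1, 4 and 7.2 and Appendix A include it, and the stability rule cannot be applied without it.

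**The concern.** Anyone who satisfies the stability rule has at least three pre-treatment AHRS ratings: Visit 1, the screening visit at which the rule was met, and Day 1. The plan uses the screening ratings only to decide eligibility. In a change score, all the visit-to-visit noise of the single Day 1 rating passes into the result with full weight. A screening rating carries further information about the participant's usual level and, being taken before randomisation, is a legitimate covariate.

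Precision is what this trial lacks. Section 11.2 calculates no sample size, describes recruitment as difficult, and relies on 16 per arm being enough for a large effect. If large means 0.8 SD of change (my assumption), the tACS-sham contrast has about 60% power at two-sided 0.05, and about 42% with Bonferroni over three pairs (45 error df).

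**Working it through.** **Inputs.** From the documents: 48 participants, 16 per arm, three arms (section 11.2); two analysed sessions and no covariate (section 11.3); at least two screening ratings (sections 4, 5.1 and 7.2). The documents give no AHRS SD, between-visit correlation, alpha or power figure, so there is no stated figure to reproduce. Correlations are assumed over a range, with equal variance at each visit, set to 1.

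Let a = corr(Day 1, Day 5), b = corr(screening, Day 5), c = corr(screening, Day 1).

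**Step 1: planned analysis to ANCOVA on Day 1.** The variance of a change score is 2(1-a). The residual variance with Day 1 as covariate is 1-a². The ratio is (1+a)/2, a cut of (1-a)/2:
- a = 0.5: 1.00 to 0.75, 25%
- a = 0.7: 0.60 to 0.51, 15%
- a = 0.8: 0.40 to 0.36, 10%

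**Step 2: add the qualifying screening score.** The further proportional cut is the squared partial correlation, (b-ac)²/[(1-a²)(1-c²)]. With all correlations equal to r this is r²/(1+r)². Example, 0.8/0.7/0.7: (0.70-0.56)²/(0.36 × 0.51) = 0.0196/0.1836 = 10.7%.

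**Step 3: small-sample charge.** With p covariates the contrast variance is inflated by 1 + p/(45-p-1). That is 1 + 1/43 = 1.023 for one and 1 + 2/42 = 1.048 for two. The second covariate therefore costs 1.048/1.023, about 2.4%, and the pair about 4.8%.

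| a / b / c | Extra cut from screening | Net of second-covariate charge | Full model against planned change score, net |
|---|---|---|---|
| 0.5 / 0.5 / 0.5 | 11.1% | 9.0% | 30% |
| 0.7 / 0.7 / 0.7 | 17.0% | 15.0% | 26% |
| 0.8 / 0.8 / 0.8 | 19.8% | 17.8% | 24% |
| 0.8 / 0.7 / 0.7 | 10.7% | 8.5% | 16% |
| 0.8 / 0.65 / 0.7 | 4.4% | 2.1% | 10% |
| 0.8 / 0.6 / 0.7 | 0.9% | -1.5% | 7% |
| 0.7 / 0.49 / 0.7 (first-order chain) | 0% | -2.4% | 11% |
| 0.8 / 0.64 / 0.8 (first-order chain) | 0% | -2.4% | 6% |

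The last column is 1 - (1-a²)(1 - extra cut)(1.048)/[2(1-a)]. For the 0.7 chain: 1 - 0.51 × 1.048/0.60 = 11%.

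**Step 4: simulation check.** In 20,000 simulated trials of 48 at r = 0.7 throughout, the variance of the tACS-sham contrast was 0.0736 (change score), 0.0638 (Day 1 covariate) and 0.0546 (both). The second step cuts 14.4%, and the two together 1 - 0.0546/0.0736 = 26%. In the 0.7 chain the second step loses 1.9%.

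**Step 5: does selecting on stability spoil the covariate?** The 20% rule was simulated under equal correlations of 0.5-0.8, with AHRS means of 22 or 28 and SDs of 5 or 7 (all assumed). The extra cut was about 14-24%, slightly higher than without selection.

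**Step 6: power.** At 0.8 SD of change, r = 0.7 throughout, Bonferroni over three pairs and the Step 3 charge included, power is 42% (change score), 48% (Day 1 covariate) and 56% (both). At unadjusted 0.05 it is 60%, 66% and 73%.

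**The case against.** The strongest reply is that the plan is valid as it stands. It defines baseline consistently as the rating just before the first stimulation, and under randomisation the change-score comparison is unbiased. In a pilot, leaving out a second baseline covariate is a choice, not a defect. That stands.

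A reader might infer that the screening score gives a 10-20% gain at no cost. The documents do not support this. They contain no AHRS correlation, and their timetable points towards fading:
- Day 5 is four days after Day 1, while the gap from the qualifying screening visit to Day 1 is not stated.
- The screening rating is further from Day 5 than from Day 1.
- The same-rater rule in section 7 covers the initial session, Day 1, Day 5 and the follow-ups but not screening visits 2-4. Section 5.3 only aims for one team member throughout.

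Modest fading takes the extra gain to 4% or below. Against that, a gain of exactly zero requires Day 1 to carry all that screening says about Day 5. This is an extreme assumption for an interview-rated scale with its own rating noise on Day 1.

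A reader might also credit the whole rise in power to the screening score. At r = 0.7 and unadjusted 0.05, 6 of the 13 points (60% to 66%) come from making Day 1 a covariate and 7 (66% to 73%) from the screening score.

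Nor is this one extra term in the existing model. The plan has no covariate, and its pairwise comparisons are separate t-tests, which would not inherit the gain. The AHRS analysis would also cease to match that of PANSS and BACS, which under Appendix A are first taken on Day 1.

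**Conclusion.** The point holds as a cheap improvement in precision. The scores exist for every eligible randomised participant, precede randomisation, and are not used in section 11.3.

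The size is conditional. The screening score's own contribution is about 11-20% at equal correlations of 0.5-0.8, about 0-11% with fading, and a net loss of about 2% if it adds nothing. The case for the full model does not rest on that contribution alone: even when screening adds nothing, it still beats the planned change score by a net 6% (Day 1-Day 5 correlation 0.8) to 11% (0.7), through Day 1 adjustment. These figures assume equal variances and linear relations.

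A reader might take this as showing that the planned test is biased or its result uninterpretable. Nothing in the documents supports that.

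**What to change.** In section 11.3, for AHRS only and before unblinding:

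1. Replace the mixed ANOVA with an ANCOVA of the AHRS after the last stimulation on arm, Day 1 AHRS and qualifying screening AHRS.
2. Take the Bonferroni-corrected pairwise arm comparisons from this model instead of separate t-tests, and state how many there are.
3. Keep Day 1 as the reference for descriptive change, so the question asked is unchanged.
4. Define the qualifying score, for instance as the rating at the screening visit where the 20% rule was met. This requires reconciling section 7.2, which compares the fourth screening visit with the second, with section 4, which speaks of consecutive administrations.
5. Describe any expected gain as conditional on correlations that this pilot will itself estimate.

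Cost: no new visits or data, two error degrees of freedom against the planned analysis (45 to 43), and about 5% variance inflation for two covariates at N=48, already charged in the net figures. The AHRS model will differ from the PANSS and BACS models, so the sentence applying one procedure to all three needs rewording.
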